#### 2.1.3.3 Other Secondary Objectives

The other efficacy secondary objectives of this study are

- To compare efficacy of plitidepsin 1.5 mg or 2.5 mg versus the control in terms of hospital readmission related to COVID-19.
- To compare efficacy of plitidepsin 1.5 mg or 2.5 mg versus the control in terms of clinical evolution.
- To compare efficacy of plitidepsin 1.5 mg or 2.5 mg versus the control in terms of the need of supplementary oxygen.
- To compare efficacy of plitidepsin 1.5 mg or 2.5 mg versus the control in terms of the need of intensification of respiratory or intensive care support.
- To compare efficacy of plitidepsin 1.5 mg or 2.5 mg versus the control in terms of the need of intensification of pharmacological therapies.
- To compare efficacy of plitidepsin 1.5 mg or 2.5 mg versus the control in terms of superinfections.
- To compare efficacy of plitidepsin 1.5 mg or 2.5 mg versus the control in terms of mortality.
- To compare efficacy of plitidepsin 1.5 mg or 2.5 mg versus the control in terms of the evolution of viral load.
- To compare efficacy of plitidepsin 1.5 mg or 2.5 mg versus the control in terms of the evolution of inflammatory markers.
- To compare efficacy of plitidepsin 1.5 mg or 2.5 mg versus the control in terms of the immune response against severe acute respiratory syndrome coronavirus 2 (SARS-CoV-2).
- To compare efficacy in the primary endpoint and describe safety/tolerability of pooled plitidepsin arms versus control.
- To compare efficacy in the primary endpoint and describe safety/tolerability between plitidepsin arms (1.5 versus 2.5 mg) in case both are significantly superior to the control.
- To explore the influence of risk factors or scores for clinical deterioration that were not individually included.
- To compare the results obtained before and after the change of the primary and key secondary endpoint (protocol v.6 versus v.7).

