# **5. Analysis Populations**

Analysis of the primary, key secondary and other time-to-event efficacy endpoints will be performed in the ITT population. Other secondary efficacy endpoints will be based on the FAS population. A sensitivity analysis will be performed for the primary endpoint, key secondary and other time-to-event efficacy endpoints in the FAS population. Supportive analyses will be performed on the Per Protocol (PP) population. Safety endpoints analyses will be based on the As Treated population.

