# 5.3 Full Analysis Set (FAS)

The FAS will consist of all randomised patients who received at least 1 dose of any study drug (plitidepsin, dexamethasone, including for patients randomised to control arm, the regulatory-approved antiviral treatments, such as, remdesivir or favipiravir) during the study and with at least 1 post-baseline clinical status collected. FAS patients are analysed according to their randomised treatment.

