The change (log10 copies/mL) from Day 1 visit to Day 8 visit will be calculated as the difference between Day 1 and Day 8 values, ie,

change from Day 1 = Day 8 value - Day 1 value

The viral load of SARS-CoV-2 (log10 copies/mL) at Day 1 and Day 8, and the change from Day 1 in SARS-CoV-2 viral load at Day 8 will be summarized using standard descriptive statistics. Data from all study visits, scheduled and unscheduled, will be listed.

CONFIDENTIAL

The change in viral load of SARS-CoV-2 at Day 8 between each dose of plitidepsin versus control arm will be compared using an analysis of covariance (ANCOVA) model fitted for the fixed effects of treatment group, the randomisation stratification factors, and the continuous fixed covariate of viral load of SARS-CoV-2 at Day 1.

The least squares (LS) means and SE for each treatment group, together with the LS mean differences, SE, 95% CIs, and 2-sided p-values for the comparison of each dose of plitidepsin versus control arm will be presented.

Median viral load of SARS-CoV-2 together with the interquartile range will be plotted at Day 1 and Day 8.

**Note**: Prior to calculation of summary statistics: any individual values below the lower limit of quantification (<LLOQ) of the PCR technique will be replaced with LLOQ/2 for the calculation of summary statistics unless it is zero.

• Percentage of patients in each study group with undetectable viral load of SARS-CoV-2 on Day 8.

The percentage of patients with undetectable viral load of SARS-CoV-2, ie, patients with viral load of SARS-CoV-2 < Limit of Detection (LOD), on Day 8 will be presented by treatment group. Clopper–Pearson 95% CI will be computed for the binomial proportions.

The difference in the percentage of patients with undetectable viral load of SARS-CoV-2 on Day 8 between each dose of plitidepsin versus control arm will be presented for each dose of plitidepsin and the exact 95% CI will be computed for the difference in the percentage.

The undetectable viral load of SARS-CoV-2 on Day 8 rate between each dose of plitidepsin versus control arm will be compared using a stratified logistic regression model. The model will be adjusted for the randomisation stratification factors. The odds ratios, 95% CIs, and 2-sided p-values for the comparison of each dose of plitidepsin versus control arm will be presented.

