The percentage of patients with a reduction  $\geq$  2-log in viral load or undetectable viral load of SARS-CoV-2 on Day 8 will be presented by treatment group. Clopper–Pearson 95% CI will be computed for the binomial proportions.

The difference in the percentage of patients with a reduction  $\geq$  2-log in viral load or undetectable viral load of SARS-CoV-2 on Day 8 between each dose of plitidepsin versus control arm will be presented for each dose of plitidepsin and the exact 95% CI will be computed for the difference in the percentage.

The reduction  $\geq$  2-log in viral load or undetectable viral load of SARS-CoV-2 on Day 8 rate between each dose of plitidepsin versus control arm will be compared using a stratified logistic regression model. The model will be adjusted for the randomisation stratification factors. The odds ratios, 95% CIs, and 2 sided p values for the comparison of each dose of plitidepsin versus control arm will be presented.

• Change in inflammatory biomarkers (CRP, ferritin, IL-1β, IL-6, IL-10, and TNFa) in each study group from baseline until Days 2, 3, 4, 8, and 31.

The Baseline value for the inflammatory biomarkers is defined as the value collected at the time of the clinic visit on Day 1. The percent change from Baseline at post-Baseline visits will be defined as:

• For CRP, ferritin, referred to the upper limit of normal (ULN)

% change from Baseline = 100\*((post-Baseline value/ULN) -(Baseline value/ULN))/(Baseline Value/ULN)

The values referred to ULN, ie, result/ULN, at baseline and at each post-Baseline visit, and the change from Baseline values will be summarized by Visit using standard descriptive statistics. The median values referred to ULN together with the interquartile ranges will be plotted over time by treatment group and visit. A spaghetti plot will also be used to represent the patient profile over time by treatment group.

 $\circ~$  For IL-1β, IL-6, IL-10, and TNFa

% change from Baseline = 100\*(post-Baseline value – Baseline value)/Baseline Value

The values at baseline and at each post-Baseline visit, and the change from Baseline values will be summarized by Visit using standard descriptive statistics.

The median values together with the interquartile ranges will be plotted over time by treatment group and visit.

A spaghetti plot will also be used to represent the patient profile over time by treatment group.

Data from all study visits, scheduled and unscheduled, will be listed.

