- **6** Serum chemistry: *Prestudy screening assessments*: ALT, AST, total bilirubin, sodium, potassium, calcium (albumin adjusted), magnesium, creatinine, calculated creatinine clearance (Cockcroft-Gault equation), CPK, and troponin (I or T according to local practice). *On study assessments*: ALT, AST, alkaline phosphatase, GGT, LDH, total bilirubin, direct bilirubin, glucose (fasting), sodium, potassium, calcium (albumin adjusted calculation), magnesium, blood urea nitrogen, creatinine, calculated creatinine clearance (Cockcroft-Gault equation), CPK, albumin, amylase, lipase, procalcitonin, troponin T (high sensitivity), and NT-pro-BNP. Note that testing to be performed by the local laboratory for screening and by central laboratory for on-study tests; tests performed within 24 hours of screening do not have to be repeated. All serum chemistry parameters will be measured at Day 1 prior to initiation of study treatment, once daily during hospitalisation, and at follow-up visits on Days 8 (±1 day) and 31 (±3 days); except, troponin T (high sensitivity), and NT-pro-BNP that will be measured on Day 1, Day 8 (±1 day), and Day 31 (±3 days).
- 7 Coagulation: D-dimer
- 8 Immunology: Proinflamatory biomarkers (CRP, ferritin, IL-1β, IL-6, IL-10, TNFα) in each study arm from baseline (Day 1 prior to start of the study treatment) to Day 4 and Days 8 (±1 day), 15 (±1 day) and 31 (±3 days).
- 9 COVID-19 screen: Qualitative PCR, antigen test to be performed by local laboratory, or any other validated method approved by the local health authority, from appropriate biological samples collected no more than 72 hours before study treatment on Day 1 for screening test to confirm COVID-19. In case more than one available, the more recent one will be selected.
- 10 COVID-19 viral load: Quantitative real-time reverse transcription polymerase-chain-reaction test (qRT-PCR) test to be performed by central laboratory from oro-nasopharyngeal exudate on Day 1 prior to initiating treatment and on Day 8 (±1 day).
- 11 Chest imaging: CT scan or x-ray will be done on Days 1, 8 (±1 day), and 31 (±3 days). Chest imaging performed within 48 hours of Day 1 is accepted and does not have to be repeated
- 12 Pregnancy test: Serum or urine pregnancy test for females of child-bearing potential, to be performed by local laboratory for screening

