### Table 14.2.3.19.1 Patients with Undetectable SARS-CoV-2 Viral Load on Day 8 (Full Analysis Set)

Variable	Plitidepsin 2.5mg	Plitidepsin 1.5mg	Control Arm
	(N=XXX)	(N=XXX)	(N=XXX)

 
Patients with Undetectable SARS-CoV-2 Viral Load on Day 8, n (%)
 
95% CI Patients with Undetectable SARS-CoV-2 Viral Load on Day 8 (%) [a]
 
Patients with Detectable or Missing SARS-CoV-2 Viral Load on Day 8, n (%)
 
Detectable SARS-CoV-2 Viral Load on Day 8, n (%)
 
Missing SARS-CoV-2 Viral Load on Day 8, n (%)
 
	xxx (xx.x) xx.x – xx.x xxx (xx.x) xxx (xx.x) xxx (xx.x)	xxx (xx.x) xx.x - xx.x xxx (xx.x) xxx (xx.x) xxx (xx.x) xxx (xx.x)	xxx (xx.x) xx.x - xx.x xxx (xx.x) xxx (xx.x) xxx (xx.x)

 
Difference of Undetectable SARS-CoV-2 Viral Load Rate on Day 8, n (%) [b]
 
95% CI for Difference of Undetectable SARS-CoV-2 Viral Load Rate on Day 8 (%) [c]
 
Adjusted Odds Ratio [d,e]
 
	XX.X XX.X – XX.X X.XXX	XX.X XX.X – XX.X X.XXX	
95% CI for Adjusted Odds Ratio [d,e]	x.xxx - x.xxx	x.xxx - x.xxx	
2-sided p-value [d]	x.xxx	x.xxx	

N = number of patients in analysis set; n = number of patients in each category. % = percentages are calculated based on N as the denominator.

CI = Confidence interval.

[a] Clopper–Pearson 95% confidence interval.

[b] Difference of Undetectable SARS-CoV-2 Viral Load Rate = Undetectable SARS-CoV-2 Viral Load Rate for the plitidepsin arm - Undetectable SARS-CoV-2 Viral Load Rate for control arm. [c] Exact 95% confidence interval.

[d] Adjusted Odds Ratio, 95% CI and 2-sided p-values based on a stratified logistic regression model with fixed effects of treatment group and randomisation stratification factors, ie, geographical region (Europe vs. Rest of the World), Charlson Comorbidity Index (0-1 vs. >1) and pre-baseline Barthel index (≥90 versus <90) as derived using the eCRF data as covariates. [e] Statistics calculated relative to Control Arm

Reference: Listing 16.2.6.8

Programming notes (not part of the table):

• Table template TEF009A.

• The displayed xxx do not reflect actual decimal precision. Please follow Section 2.11 for rounding rules.

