### Table 14.2.3.19.2 Patients with a Reduction ≥ 2-log in Viral Load or Undetectable SARS-CoV-2 Viral Load on Day 8 (Full Analysis Set)

Variable	Plitidepsin 2.5mg (N=XXX)	Plitidepsin 1.5mg (N=XXX)	Control Arm (N=XXX)
Patients with a Reduction $\geq$ 2-log in Viral Load or Undetectable SARS-CoV-2 Viral Load on Day 8, n (%)	xxx (xx.x)	xxx (xx.x)	xxx (xx.x)
95% CI Patients with a Reduction $\geq$ 2-log in Viral Load or Undetectable SARS-CoV-2 Viral Load on Day 8 (%) [a]	XX.X - XX.X	XX.X – XX.X	XX.X - XX.X
Patients with Detectable and a Reduction < 2-log in Viral Load or Missing SARS-CoV-2 Viral Load on Day 8, n (%)	xxx (xx.x)	xxx (xx.x)	xxx (xx.x)
Difference of Reduction $\geq$ 2-log in Viral Load or Undetectable SARS-CoV-2 Viral Load Rate on Day 8, n (%) [b]	XX.X	xx.x	
95% CI for Difference of Reduction ≥ 2-log in Viral Load or Undetectable SARS-CoV-2 Viral Load Rate on Day 8 (%) [c]	XX.X – XX.X	XX.X – XX.X	
Adjusted Odds Ratio [d,e]	X.XXX	X.XXX	
2-sided p-value [d]	x.xxx - X.XXX X.XXX	x.xxx - X.XXX X.XXX	

N = number of patients in analysis set; n = number of patients in each category. % = percentages are calculated based on N as the denominator.

CI = Confidence interval.

[a] Clopper-Pearson 95% confidence interval.

[b] Difference of Reduction  $\geq$  2-log in Viral Load or Undetectable SARS-CoV-2 Viral Load Rate = Reduction  $\geq$  2-log in Viral Load or Undetectable SARS-CoV-2 Viral Load Rate for the plitidepsin arm - Reduction  $\geq$  2-log in Viral Load or Undetectable SARS-CoV-2 Viral Load Rate for control arm.

[c] Exact 95% confidence interval.

[d] Adjusted Odds Ratio, 95% CI and 2-sided p-values based on a stratified logistic regression model with fixed effects of treatment group and randomisation stratification factors, ie, geographical region (Europe vs. Rest of the World), Charlson Comorbidity Index (0-1 vs. >1) and pre-baseline Barthel index ( $\geq$ 90 versus <90) as derived using the eCRF data as covariates.

[e] Statistics calculated relative to Control Arm

Reference: Listing 16.2.6.8

Programming notes (not part of the table):

• Table template TEF009A.

• The displayed xxx do not reflect actual decimal precision. Please follow Section 2.11 for rounding rules.

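### The two Day 8 virological endpoints count patients already undetectable on Day 1 as successes and do not adjust for Day 1 viral load, which dilutes the comparison and loses precision

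*SAP*

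**What the plan says.** The objective in SAP section 2.1.3.3 is to compare each plitidepsin dose "versus the control in terms of the evolution of viral load". Section 7.6.2.3 addresses it with one continuous and two binary analyses.

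- **Continuous:** change from Day 1 to Day 8, by an ANCOVA with treatment, the stratification factors and Day 1 viral load as a continuous covariate.
- **Binary 1:** the percentage of "patients with viral load of SARS-CoV-2 < Limit of Detection (LOD), on Day 8 will be presented by treatment group".
- **Binary 2:** the percentage with a reduction of at least 2 log "or undetectable viral load of SARS-CoV-2 on Day 8 will be presented by treatment group".

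Both binary endpoints are compared by a logistic model adjusted for the stratification factors only. Section 5 states "Other secondary efficacy endpoints will be based on the FAS population", and section 5.3 states "The FAS will consist of all randomised patients who received at least 1 dose of any study drug", with at least one post-baseline clinical status. The FAS has no virological criterion. The shells for Tables 14.2.3.19.1 and 14.2.3.19.2 use N, the whole arm, as denominator. They place missing Day 8 samples with the failures: "Patients with Detectable or Missing SARS-CoV-2 Viral Load on Day 8, n" and "Patients with Detectable and a Reduction < 2-log in Viral Load or Missing SARS-CoV-2 Viral Load on Day 8, n".

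Under Appendix 4, footnote 9, COVID-19 is confirmed by a local PCR, antigen or other validated test, on samples "collected no more than 72 hours before study treatment on Day 1 for screening test to confirm COVID-19". Under footnote 10, viral load comes from a separate central quantitative PCR on Day 1, before treatment, and on Day 8.

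**The concern.** A patient can test positive locally up to three days before Day 1 and be below the LOD in the central Day 1 sample. If that patient is again below the LOD on Day 8, both binary endpoints record a success although nothing was cleared on study. Such patients add the same amount to the rate in every arm and so pull the treatment difference toward zero.

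The logistic models also leave out Day 1 viral load, a baseline variable that the SAP already collects and uses in the companion ANCOVA. The treatment of serology in the same section is a useful contrast: a patient already IgG-positive at baseline must show at least a two-fold rise to count as a response. The virology endpoints have no such baseline condition.

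At stake are the sensitivity and precision of the two binary tests of antiviral effect.

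**Working it through.** The SAP gives no rate, effect size or power for these endpoints, so there is no plan figure to reproduce.

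**Inputs from the SAP:** the endpoint rules, FAS, denominators and covariates above; the 2-sided 0.05 level (section 7.1); 203 patients per arm planned (section 2.3); recruitment stopped before 33% of events (section 8).

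**Assumptions, not in the SAP:** share undetectable on Day 1, u = 10-30%; Day 8 undetectable rate among patients detectable on Day 1, c = 30% on control and 45% on drug; Day 8 undetectable rate among patients undetectable on Day 1, r = 95% in all arms; no missing samples.

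**Dilution.** The rate in an arm is (1-u)c + u·r. With u and r equal between arms, the u·r terms cancel and the difference is (1-u) × (0.45 - 0.30), whatever r is.

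| u | Control | Drug | Difference (points) | OR |
|---|---|---|---|---|
| 0 | 30.0% | 45.0% | 15.0 | 1.91 |
| 10% | 36.5% | 50.0% | 13.5 | 1.74 |
| 20% | 43.0% | 55.0% | 12.0 | 1.62 |
| 30% | 49.5% | 60.0% | 10.5 | 1.53 |

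**Power** (two proportions, unadjusted). Restriction keeps 203 × (1-u) patients per arm.

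| u | All FAS | Restricted to Day 1 detectable |
|---|---|---|
| 10% | 78.6% | 84.5% |
| 20% | 67.8% | 80.0% |
| 30% | 56.6% | 74.5% |

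With 50% versus 65% instead, the figures at u = 20% are 71.9% and 78.3%. The restricted analysis had more power in every scenario tried with u above zero, despite fewer patients.

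**Chance imbalance.** The 95% range for the between-arm difference in u is ±1.96 × √(2u(1-u)/n). At u = 20% it is ±7.8 points with n = 203. The number actually enrolled is not stated. The planned event fraction suggests 175 / (530/609) / 3, about 67 per arm, at 33% of events. With event fractions of 80% or 70% the same sum gives 73 or 83. At n = 67 the range is ±13.5 points. Multiplying by r - c = 0.65, the unadjusted rate difference moves by about ±5.1 points (n = 203) or ±8.8 points (n = 67).

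**What an imbalance can do with no drug effect.** Take 15% versus 25% undetectable on Day 1, all staying so, and c = 30% in both arms. The rates are 0.15 + 0.85 × 0.30 = 40.5% and 0.25 + 0.75 × 0.30 = 47.5%. With 67 per arm the standard error is √(2 × 0.44 × 0.56 / 67) = 0.086, so z = 0.07/0.086 = 0.82 and p is about 0.41. The 95% interval is about -10 to +24 points.

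**The case against.** **Endpoint definition.** The first endpoint is listed in section 3.5 as a Day 8 status, and text and shell implement it as listed. Replacing the all-FAS analysis would redefine it. This stands, so the restricted analysis should be added rather than substituted. The criticism fits the 2-log composite more closely, since that is worded as a change from Day 1.

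**Coverage elsewhere.** The ANCOVA already addresses evolution with Day 1 adjustment, and Day 1 load is summarised by arm in Table 14.2.3.18, plotted and listed. An imbalance would therefore be visible. That limits the harm but does not adjust the two binary comparisons. The Day 1 viral load subgroups do not help either, as they are planned for the primary endpoint and for safety.

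**Frequency.** How many patients are undetectable on Day 1 is unknown. The subgroup below 4 log10 is not the same as undetectable. The mock row in Listing 16.2.2.1 shows more than 10 days since symptom onset as an unmet entry criterion, so the corresponding subgroup is weak evidence that late presenters were expected. What the SAP supports is that such patients can occur.

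**Stronger readings.** A reader might infer that the comparison is biased in the drug's favour or could manufacture an effect. The plan does not support this. Randomisation balances Day 1 status in expectation, the ordinary interval and p-value allow for chance imbalance, and the 7-point null example is far from significant. A reader might also treat about 67 per arm as the trial's size, or regard patients undetectable on Day 1 as uninformative. The first is an inference from the event fraction; the second fails because a patient negative on Day 1 can be positive on Day 8.

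Counting a missing Day 8 sample as a failure affects every patient and is a separate matter.

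**Conclusion.** The point holds as an efficiency and interpretation problem. Both Day 8 endpoints credit patients who were below the LOD on Day 1 and remain so, and both logistic models omit a baseline covariate that the companion ANCOVA uses.

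The systematic consequence is dilution by (1-u): an assumed 15-point difference becomes 13.5 to 10.5 points for u between 10% and 30%. This rests on patients undetectable on Day 1 behaving alike in all arms. The size is illustrative because neither u nor the clearance rates are in the SAP. Chance imbalance in u is left unadjusted, which costs precision but does not inflate type I error.

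These are other secondary endpoints outside the Hochberg procedure, so the primary and key secondary conclusions are unaffected.

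**What to change.** In section 7.6.2.3 and Tables 14.2.3.19.1 and 14.2.3.19.2:

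1. Add continuous Day 1 log10 viral load as a covariate to both logistic models, as in the ANCOVA.
2. Add an analysis of both endpoints restricted to FAS patients with detectable Day 1 virus (at or above the LLOQ for the 2-log criterion), and keep the all-FAS analysis beside it. The Day 1 sample precedes treatment, so the drug cannot influence this selection.
3. Show by arm the numbers undetectable and the numbers missing on Day 1.
4. State how missing Day 1 samples are handled, so that the covariate does not silently drop patients from the model.

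The cost is some SAP and shell wording, one filter, one covariate already collected and a few table rows. The restricted analysis has a smaller denominator. The addendum dates database lock at 26 April 2023, so anything added now should be labelled post hoc, like the addendum's other outputs.

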• Change respect to baseline in individual serological assessments.

The percentage of patients with a serologic response anti-SARS-CoV-2 at Day 31 will be presented by treatment group. Clopper–Pearson 95% CI will be computed for the binomial proportions.

The Baseline value for the serologic response anti-SARS-CoV-2 is defined as the immunoglobulin (Ig)G Antibodies quantification value collected at the time of the clinic visit on Day 1.

Patients are considered to have a serologic response anti-SARS-CoV-2 if:

- Baseline IgG Antibodies quantification is interpreted as negative (e.g. <0.8), borderline (e.g. ≥0.8 and <1.1) or missing and increases above the established boundary (e.g. ≥1.1), following study drug administration.

- Baseline IgG Antibodies are positive and the result at Day 31 sample is at least two-folds greater than the baseline sample.

All of the other options are considered as non-serologic response.

Cutoffs for IgG Antibodies quantification will be selected at the analysis time based on the latest available specifications of the selected technology.

The difference in the percentage of patients with a serologic response anti-SARS-CoV-2 between each dose of plitidepsin versus control arm will be presented for each dose of plitidepsin and the exact 95% CI will be computed for the difference in the percentage.

The percentage of patients with a serologic response anti-SARS-CoV-2 between each dose of plitidepsin versus control arm will be compared using a stratified logistic regression model. The model will be adjusted for the randomisation stratification factors. The odds ratios, 95% CIs, and 2-sided pvalues for the comparison of each dose of plitidepsin versus control arm will be presented.

The IgG Antibodies quantification values at baseline and at Day 31 visit, and the change from Baseline in IgG Antibodies quantification values will be summarized using standard descriptive statistics.

The percent change in IgG Antibodies quantification from Baseline at Day 31 visit will be defined as:

% change from Baseline = 100\*(Day 31 value – Baseline value)/Baseline Value

Data from all study visits, scheduled and unscheduled, will be listed.

• To compare efficacy in the primary endpoint and describe safety/tolerability of pooled plitidepsin arms versus control.

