### Table 14.2.3.21.1 Patients with a Serologic Response Anti-SARS-CoV-2 (Full Analysis Set)

Variable	Plitidepsin 2.5mg	Plitidepsin 1.5mg	Control Arm
	(N=XXX)	(N=XXX)	(N=XXX)
Patients at Day 31 with serologic assessment, n1	xxx	xxx	XXX
Patients with a Serologic Response Anti-SARS-CoV-2, n (%)	xxx (xx.x)	xxx (xx.x)	xxx (xx.x)
95% CI Patients with a Serologic Response Anti-SARS-CoV-2 (%) [a]	xx.x – xx.x	xx.x - xx.x	xx.x - xx.x
Patients without a Serologic Response Anti-SARS-CoV-2, n (%)	xxx (xx.x)	xxx (xx.x)	xxx (xx.x)
Difference of Serologic Response Anti-SARS-CoV-2 Rate, n (%) [b]	XX.X	XX.X	
95% CI for Difference of Serologic Response Anti-SARS-CoV-2 Rate (%) [c]	XX.X – XX.X	XX.X – XX.X	
Adjusted Odds Ratio [d,e]	X.XXX	x.xxx	
95% CI for Adjusted Odds Ratio [d,e]	X.XXX - X.XXX	x.xxx - x.xxx	
2-sided p-value [d]	X.XXX	x.xxx	

N = number of patients in analysis set; n = number of patients in each category; n1 = number of patients with data available at timepoint; % = percentages are calculated based on n1 as the denominator; CI = Confidence interval.

Notes: Serologic Response Anti-SARS-CoV-2:

• Baseline IgG Antibodies quantification is interpreted as negative (e.g. <0.8), borderline (e.g. ≥0.8 and <1.1) or missing and increases above the established boundary (e.g. ≥1.1), following study drug administration.

• Baseline IgG Antibodies are positive and the result at Day 31 sample is at least two-folds greater than the baseline sample.

[a] Clopper-Pearson 95% confidence interval.

[b] Difference of Serologic Response Anti-SARS-CoV-2 Rate = Serologic Response Anti-SARS-CoV-2 Rate for the plitidepsin arm - Serologic Response Anti-SARS-CoV-2 Rate for control arm. [c] Exact 95% confidence interval.

[d] Adjusted Odds Ratio, 95% CI and 2-sided p-values based on a stratified logistic regression model with fixed effects of treatment group and randomisation stratification factors, ie, geographical region (Europe vs. Rest of the World), Charlson Comorbidity Index (0-1 vs. >1) and pre-baseline Barthel index (≥90 versus <90) as derived using the eCRF data as covariates. [e] Statistics calculated relative to Control Arm

Reference: Listing 16.2.6.9

- Table template TEF009A.
- The displayed xxx do not reflect actual decimal precision. Please follow Section 2.11 for rounding rules.

	Plitideps (N=2	in 2.5mg XXX)	Plitideps (N=2	sin 1.5mg XXX)	Con (N	trol Arm =XXX)
Visit		% Change from		% Change from		% Change from

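### A missing Day 1 IgG is treated as non-positive, so Day 31 positivity alone makes such a patient a serologic responder

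*SAP*

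**What the plan says.** SAP Section 7.6.2.3, under the change from baseline in individual serological assessments, takes the Day 1 sample as the reference: "The Baseline value for the serologic response anti-SARS-CoV-2 is defined as the immunoglobulin (Ig)G Antibodies quantification value collected at the time of the clinic visit". Two ways to be a responder follow.

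- The baseline is negative, borderline "or missing and increases above the established boundary" after study drug.
- "Baseline IgG Antibodies are positive and the result at Day 31 sample is at least two-folds greater than the baseline sample".

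The section closes with "All of the other options are considered as non-serologic response".

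The shell for Table 14.2.3.21.1 repeats both criteria in its footnote, including the treatment of a missing baseline. Its first row is "Patients at Day 31 with serologic assessment, n1", and "percentages are calculated based on n1 as the denominator". A Day 1 value is not needed to be counted.

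The result is used for inference: "The percentage of patients with a serologic response anti-SARS-CoV-2 between each dose of plitidepsin versus control arm will be compared using a stratified logistic regression". The output is odds ratios, confidence intervals and two-sided p-values.

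**The concern.** The endpoint is a change from baseline, and no increase can be observed without a baseline. For a patient with no Day 1 sample, the first criterion reduces to being positive on Day 31. That is a weaker test than the two-fold rise asked of a patient known to be positive on Day 1.

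The SAP itself expects such patients. Section 7.6.4 defines subgroups by Day 1 IgG (positive or non-positive) and by vaccination status, so treating every missing baseline as non-positive assumes away a status that the plan regards as variable. According to the schedule in Appendix 4, the IgG test is done only on Day 1 and Day 31, so no other scheduled sample can replace a lost Day 1 value.

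The neighbouring viral load tables go the other way. Tables 14.2.3.19.1 and 14.2.3.19.2 group a missing Day 8 value with non-response, and the first of these gives it a separate row. In the serology table a missing value can produce a response, and no row shows how often.

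At stake are the accuracy of the reported response rates and, if missingness or baseline serostatus differs between arms, the odds ratios.

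**Working it through.** The SAP states no expected rate, sample size or missing-data rate for this endpoint, so there is no figure to reproduce. The check has two parts: the logic of the rule, and an illustration of size under assumed inputs.

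**Logic.** Take the SAP's example boundary of 1.1.

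| Day 1 IgG | Day 31 IgG | Classification |
|---|---|---|
| Negative or borderline | at or above 1.1 | Responder |
| Positive | at least twice baseline | Responder |
| Positive | positive, less than twice baseline | Non-responder |
| Missing | at or above 1.1 | Responder |
| Missing | below 1.1 | Non-responder |

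The third and fourth rows can describe the same patient, with and without a Day 1 sample. A patient with a missing baseline who was truly negative and seroconverted is classified correctly. The error is confined to those already seropositive without a two-fold rise.

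**Size, first set of assumptions.** Let *m* be the share with a missing baseline among patients with a Day 31 result, *r* the true response rate, and 97% the share of Day 31 samples above the boundary. Assume that baselines are missing at random.

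- Reported rate = (1 − m) × r + m × 0.97, so inflation = m × (0.97 − r).
- m = 5%, r = 70%: 0.05 × 0.27 = 1.35 points.
- m = 15%, r = 50%: 0.15 × 0.47 = 7.05 points.
- If missingness differs by 10 points between arms with no true effect, the difference shifts by 0.10 × (0.97 − r): 0.10 × 0.27 = 2.7 points at r = 70%, and 0.10 × 0.47 = 4.7 points at r = 50%.
- If missingness and Day 31 positivity are equal in both arms, the reported difference is (1 − m) × (r₁ − r₂). A true difference is diluted and none is created.

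**Size, second set of assumptions.** Let π be the share truly positive on Day 1, *f* the share of those with at least a two-fold rise, and *q* = 99% the share of those still above the boundary on Day 31. Assume 95% seroconversion among the non-positive.

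- Inflation = m × π × (q − f).
- With π = 50% and f = 50%, the true rate is 0.5 × 0.5 + 0.5 × 0.95 = 72.5%. Inflation is 0.05 × 0.5 × 0.49 = 1.2 points at m = 5%, 2.5 points at m = 10% and 4.9 points at m = 20%.
- Over π = 30% to 80%, f = 20% to 80% and m = 5% to 20%, the smallest value is 0.05 × 0.3 × 0.19 = 0.3 points and the largest is 0.20 × 0.8 × 0.79 = 12.6 points.
- A 10-point imbalance in missingness gives 0.10 × 0.3 × 0.19 = 0.6 points to 0.10 × 0.8 × 0.79 = 6.3 points.

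The two sets agree on direction and rough order. Neither is an estimate for this trial.

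**The case against.** The strongest reply is that this may matter little. The Day 1 sample is planned before study treatment starts, so treatment received cannot cause it to be missing, and nothing in the plan points to unequal missingness. With balanced missingness the rule dilutes a difference. The endpoint is one of many other secondary ones, and the multiplicity procedures for the primary and key secondary endpoints do not cover it. The count of missing baselines can also be worked out indirectly. Table 14.2.3.21.2 gives, by arm, the number with a Day 31 percent change, which needs both samples. That number can be set against n1, and Listing 16.2.6.9 shows each patient's results. Finally, the database was locked on 26 April 2023 (addendum, Section 1) in an open-label trial, so replacing a prespecified definition now would itself be a post-hoc change.

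Most of this stands, and it limits the severity and shapes the remedy. It does not answer the misclassification: the rule as written gives two results for one clinical course, and a reader of the response table would not see how many patients this affects.

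Two stronger readings are tempting and should not be drawn.

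- A reader might infer that text and shell conflict on the denominator, with a missing Day 31 sample a non-response in one and an exclusion in the other. The closing sentence of the definition does not mention missing Day 31 samples, and SAP Section 7.1 lets a table shell set a denominator other than the analysis population. The shell does so with n1.
- A reader might infer that response is overstated in every arm. That holds only where an arm has missing baselines in patients who were seropositive without a two-fold rise, and the documents do not show how many there are.

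**Conclusion.** The point stands as a misclassification rule of unknown size. Section 7.6.2.3 and the footnote of Table 14.2.3.21.1 make Day 31 positivity sufficient for response when the Day 1 value is missing, although a known-positive patient needs a two-fold rise. Under the first set of assumptions the inflation is about 1 to 7 points; the wider second set gives 0.3 to 12.6. A between-arm shift, about 2.7 to 4.7 points per 10-point imbalance in missingness under the first set, arises only if missingness or baseline serostatus differs by arm. All these sizes rest on assumed missingness, seropositivity and response rates. The primary and key secondary analyses are not affected. The rule should be changed or supplemented, but it does not threaten the trial's main conclusions.

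**What to change.** - Delete the words *or missing* from the first responder criterion in Section 7.6.2.3 and in the Table 14.2.3.21.1 footnote.
- Base the response rate and the logistic model on patients with both Day 1 and Day 31 IgG, and say so in text and shell.
- Add a row with the number of missing baselines by arm.
- Keep the current rule as a labelled sensitivity row.

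As the database is locked, an equivalent course is to leave the prespecified analysis in place and add the paired-sample analysis and the counts beside it as a labelled post-hoc output. The addendum allows additional tables.

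The cost is one phrase, a footnote and a few table rows. The paired analysis has slightly fewer evaluable patients and assumes that baselines are missing at random, which the counts by arm would help the reader to judge.
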